Our methodology is a prospective randomized controlled trial to evaluate the effect of maternal immunization with pneumococcal vaccine on the filial antibody response to pneumococcal conjugate vaccine given at 6, 10 and 14 weeks of age. The primary outcome is the antibody titer to selected serotypes of pneumococcal vaccine and to tetanus toxoid. We will specifically compare the association between the levels of antibodies at birth and 6 weeks of age (passive maternal antibodies) with the level at 18-20 weeks of age (filial active antibody response) and at 9 months of age of the infant. As a secondary objective, we will determine the ability of infants in Dhaka to respond to new pneumococcal conjugate vaccine when given in the W.H.O. schedule without the

maternal dose. We will also assess the effect of the infants' serum IgG antibody and maternal IgA antibody in breast milk on colonization of the infants with pneumococci.

If we can show that the strategy of maternal + infant pneumococcal immunization to have a better immune response, then this strategy could be considered an appropriate immunization strategy for the regions to prevent early infant pneumococcal disease. Pneumococcal vaccines are licensed and readily available, and delivery systems to immunize pregnant women and infants are functioning in many developing countries. This strategy is operationally feasible and could have a substantial effect on early infant mortality.

KEY PERSONNEL (List names of all investigators including PI and their respective specialties)

Name	Professional Discipline/ Specialty	Role in the Project
ICDDR,B		
1. [name]	Epidemiology	Principal - Investigator
2. [name] [name]	Epidemiology	Co-investigator
3. [name]	Epidemiology	Co-investigator
3. [name]	Microbiology	Co-investigator
4.To be identified	Immunology	Co-investigator
Johns Hopkins		
1. [name]	Epidemiology	Co- principal - Investigator
2. [name]	Immunology .	Co-investigator
3.[name]	Immunology	Co-investigator
	67	2 2 22.18 01101

DESCRIPTION OF THE RESEARCH PROJECT

Hypothesis to be tested:

To determine the immunogenicity and safety of conjugate pneumococcal vaccine in infants of mothers who have been immunized with pneumococcal polysaccharide vaccine.

Specific Aims:

The specific objectives of the revised project are:

Primary Objectives

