The primary outcome measures are the infant serum IgG antibody titers to specific capsular pneumococcal polysaccharide, and to the protein carrier moiety of the pneumococcal conjugate vaccine. These data will be generated on coded specimens by the laboratory and reported as microgram per ml for each subject. The comparisons of interest are of the antibody concentrations at birth, which represents passively acquired maternal antibody; and the antibody concentrations after 3 doses of immunization at 18 weeks of age, which represent the active filial antibody response.

Sample size estimate

In order to estimate the sample size required to answer the primary research questions posed in the objectives of this proposal, we used standard sample size formulae and pneumococcal antibody geometric mean and standard deviation data from our studies of the 5 valent Praxis glycoprotein conjugate pneumococcal vaccine given to US infants at 2, 4 and 6 months of age (table 2 below).

Table 1 ANTIBODY MEAN AND SD DATA^{a)}

serotype	N	IgG GMT	mean log	std. dev. of logs	
19F	43	3.6 μg/ml	0.55882	0.605756	
6B	45	2.3 μg/ml	0.36080	0.767809	

^{a)}values are for sera collected at 7 months of age, after 3 doses given at 2, 4 and 6 months of age to US infants

Table 2 utilizes the data in table 1 to show the number of subjects per group which are required to detect the specified differences between the antibody GMTs of groups 1 and 2. Since one goal of the project is to determine if a study group 2 has a lower antibody titer than group 1, a one-sided test of significance is appropriate, however, a 2-sided test allows full examination of the relationships.. A sample size of 63 in each group will allow us to detect a difference of 50% in the final geometric mean titers.

Table 2 SAMPLE SIZE ESTIMATES

group GMT (μg/ml)		Dif	Difference			Number each in group a)		
_ A	B	%	Fold		1 sided	2 sided		
1.8	3.6	-50%	0.5		50	63		
2.5	3.6	-30%	0.7		185	235		
2.7	3.6	-25%	0.75		285	362		
2.9	3.6	-20%	0.80		445	565		

 $^{^{}a)}$ assuming alpha = 0.05, beta = 0.20, power = 80%.

We had 79% rate of completion in our previous study in Dhaka. If 30% of enrolled subjects do not complete the study, $(63 \div 0.7 =)$ 90 subjects will need to be enrolled in each group, for a project total of 180 mother-infant pairs. (Appendix 3)

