Antibody assay validity and variability: Because antibody titers are the principal outcomes of this studies, we have instituted procedures to ensure validity and to reduce the variability of antibody assays. The ELISA for pneumococcal antibody has been standardized using the CDC/WHO standard assay procedures and FDA reference serum by [name] at Johns Hopkins University. Interassay variability is now assessed by running a local control serum (89-1C) on each plate to measure day to day variations. During a recent study of pneumococcal immunization of adults with and without HIV infection the co-efficients of variation for serotypes 6B, 14, 18C, 19F, and 23F were 30%, 12%, 11%, 12%, 16%, respectively. These values were typical for variation as reported by other centers, including the observation that type 6B has greater variability than the remaining serotypes. The laboratory will receive the serum coded and thus they will remain blinded to the code assignments.

Data analysis (see appendix 2)

Sera with undetectable antibody will be assigned half the lower limit of detection for the purposes of calculating means. Because the distributions of antibody titers and of the increases in titer (post-immunization antibody level divided by pre-immunization antibody level) are likely to be positively skewed, the values will be log-transformed to approximate a normal distribution for statistical analyses. The antilogarithms of the means of the log-transformed values will be reported as geometric mean titers (GMT) or as geometric mean increases. Continuous variables will be compared between groups by two-sided T-test or Mann-Whitney U test within groups by the paired T-test, and associations of continuous variables will be assessed by Pearson's correlation coefficient or the Spearman rank correlation test. The Chi Square or Fisher's exact test will be used to compare proportions between groups.

The gestational age of the infants will be estimated by two methods. The mothers will be asked the date of the first day of their last menstrual period, from which we will calculate the duration of the gestation period. In addition, each child will be examined within 48 hours of birth using the method of Ballard to assess the neuromuscular and physical maturity of the infant (25). The Ballard technique assigns a score for neuromuscular and physical maturation and allows an estimation of gestational age.

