In order to determine the success of the randomization procedure, the following variables of the mothers and infants will be compared to determine if the means or proportions are significantly different between the groups: maternal age, height, education, and parity, household size, gestational age at immunization, gestational age at delivery, immunization-birth delivery, birth weight, percent of infants with birth weight less than 2.5 kg, and less than 37 weeks gestation. The geometric mean pneumococcal antibody titers before immunization and at the time of delivery will be compared between mothers in the study groups, by ANOVA. Similarly, the infants' antibody titers to pneumococcal polysaccharide, diphtheria toxoid and tetanus toxoid will be compared between the three study groups in cord, 6 week and 18 week specimens by ANOVA test. The groups will be compared with respect to key characteristics to assess randomization. Proportions with adverse events and proportions seroconverting will be compared using chi-square tests.

We will compare the final infant pneumococcal antibody GMT between study group 1 and 2 to assess the effect of passive antibody on the filial antibody response to three doses of glycoprotein conjugate pneumococcal vaccine.

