Appendix 3 Two-Sample T-Test Power Analysis

Numeric Results for Two-Sample T-Test

Null Hypothesis: Mean1=Mean2. Alternative Hypothesis: Mean1>Mean2 The standard deviations were assumed to be known and equal.

		Α	llocation	•					
Power	N1	N2	Ratio	Alpha	Beta	Mean1	Mean2	S1	S2
0.80286	63	63	1.00	0.02500	0.19714	0.559	0.258	0.601	0.601
0.80514	50	50	1.00	0.05000	0.19486	0.559	0.258	0.601	0.601

Two-Sample T-Test Power Analysis

Numeric Results for Two-Sample T-Test

Null Hypothesis: Mean1=Mean2. Alternative Hypothesis: Mean1>Mean2 The standard deviations were assumed to be known and equal.

			Allocation						
Power	N1	N2	Ratio	Alpha	Beta	Mean1	Mean2	S1	S2
0.80000	40	40	1.00	0.02500	0.20000	0.559	0.182	0.601	0.601
0.80000	50	50	1.00	0.02500	0.20000	0.559	0.222	0.601	0.601
0.80000	60	60	1.00	0.02500	0.20000	0.559	0.251	0.601	0.601
0.80000	70	70	1.00	0.02500	0.20000	0.559	0.274	0.601	0.601
0.80000	80	80	1.00	0.02500	0.20000	0.559	0.293	0.601	0.601
0.80000	90	90	1.00	0.02500	0.20000	0.559	0.308	0.601	0.601
0.80000	100	100	1.00	0.02500	0.20000	0.559	0.321	0.601	0.601
0.80000	40	40	1.00	0.05000	0.20000	0.559	0.225	0.601	0.601
0.80000	50	50	1.00	0.05000	0.20000	0.559	0.260	0.601	0.601
0.80000	60	60	1.00	0.05000	0.20000	0.559	0.286	0.601	0.601
0.80000	70	70	1.00	0.05000	0.20000	0.559	0.306	0.601	0.601
0.80000	80	80	1.00	0.05000	0.20000	0.559	0.323	0.601	0.601
0.80000	90	90	1.00	0.05000	0.20000	0.559	0.336	0.601	0.601
0.80000	100	100	1.00	0.05000	0.20000	0.559	0.347	0.601	0.601

M2 vs N1 by Alpha with M1=0.559 S1=0.601 S2=0.601 Power=0.80 N2=N1 1-Sided T Tes

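### The 18-week comparison is sized on a halved titer and analysed by a difference test, with no margin or rule for concluding that maternal antibody does not interfere, and no link to the better response on which the strategy rests

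*Protocol*

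**What the plan says.** **Question.** The opening rationale notes that maternal antibody is known to depress infant responses to some other vaccines, and concludes that the feasibility of combined passive and active immunization has to be tested. The primary objective under Specific Aims is neutral: whether maternal antibody influences the immunogenicity and safety of the conjugate vaccine.

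**Condition for the strategy.** The opening summary makes its recommendation conditional: "If we can show that the strategy of maternal + infant pneumococcal immunization to have a better immune response". It gives no time point, minimum gain or margin.

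**Sizing.** Sample size estimate starts from "Since one goal of the project is to determine if a study group 2 has a lower antibody titer than group 1". Group 2 is the maternal-plus-infant arm in Appendix 1. Table 2 lists only reductions, from 50% to 20%. Appendix 3 prints "Null Hypothesis: Mean1=Mean2. Alternative Hypothesis: Mean1>Mean2".

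**Sidedness.** The same section says "a one-sided test of significance is appropriate, however, a 2-sided test allows full examination of the relationships". The adopted 63 per group is the two-sided column of Table 2; the one-sided figure is 50.

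**Analysis.** Data analysis states: "Continuous variables will be compared between groups by two-sided T-test or Mann-Whitney U test". For the final titers: "We will compare the final infant pneumococcal antibody GMT between study group 1 and 2 to assess the effect of passive antibody". The Protocol states no non-inferiority or equivalence margin; the only null hypothesis is equality of means.

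**The concern.** Three parts of the plan point in different directions. The sizing looks for harm, the recommendation looks for superiority, and the scientific question is whether the infant response is preserved. If the maternal dose does not interfere, the 18-week titers should be about equal, and the most likely result is no significant difference. The plan gives that result no meaning. A test of equality that fails to reject does not show that a meaningful loss has been excluded. Only an interval read against a stated margin can do that.

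What is at stake is the main message of the trial. Its most plausible favourable outcome could be read as reassurance when the data are still compatible with more than a halving of the titer.

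**Working it through.** **Inputs.** SD of log10 titer 0.601 (Appendix 3; Table 1 gives 0.605756 for 19F) and 0.767809 (Table 1, 6B). Final GMT 3.6 against 1.8, so δ = log10(2) = 0.301. Two-sided alpha 0.05, 80% power, 63 per group, 30% dropout.

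**Step 1: reproduce the plan's figures.** n = 2(z₁₋α/₂ + z₀.₈₀)²·SD²/δ² = 2 × (1.960 + 0.842)² × 0.601² / 0.301² = 62.6, so 63. With z = 1.645 the one-sided figure is 50. Normal-approximation power is 0.803 and 0.805, matching Appendix 3. Enrolment is 63/0.7 = 90. The stated figures are confirmed. With SD 0.605756 the two-sided n is 64, an immaterial difference.

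**Step 2: what the planned test detects.** SE = 0.601 × √(2/63) = 0.107. Using the noncentral t distribution with 124 df and ncp = log10(ratio)/SE:

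| True GMT ratio (group 2 / group 1) | Group 2 significantly lower | Group 2 significantly higher | Not significant |
|---|---|---|---|
| 0.5 | 80% | 0% | 20% |
| 0.6 | 54% | 0% | 46% |
| 0.7 | 30% | 0% | 70% |
| 1.0 | 2.5% | 2.5% | 95% |
| 1.5 | 0% | 37% | 63% |
| 2.0 | 0% | 80% | 20% |

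The test is symmetric on the log scale: a doubling has the same power as a halving. With the 6B SD, power for a twofold change in either direction is 59%.

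**Step 3: what a non-significant result leaves open.** The 95% half-width is 1.979 × 0.107 = 0.212 log10, a factor of 1.63.
- Observed ratio 1.0: interval 0.61 to 1.63, which excludes a halving.
- Observed ratio just short of significance: about 0.61, with a lower limit near 0.38, which does not exclude a halving.

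Both are reported as not significant, yet they carry quite different information about interference.

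**Step 4: the same data read against a margin.** The Protocol gives no margin, so these are assumptions. They use 80% power, a true ratio of 1 and a two-sided 95% interval.

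| Margin | SD | n per group | Enrolled per group (÷ 0.7) |
|---|---|---|---|
| 0.50 | 0.601 | 63 | 90 |
| 0.67 (1.5-fold) | 0.601 | 183 | 262 |
| 0.80 (1.25-fold) | 0.601 | 604 | 863 |
| 0.50 | 0.768 | 103 | 148 |

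At 63 per group and a 0.5 margin, the observed ratio must exceed about 0.5 × 1.63 = 0.81 (SD 0.601). Power at a true ratio of 1 is 80% with SD 0.601 and 59% with the 6B SD. A true halving passes 2.5% of the time.

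**The case against.** The strongest reply is that the stated test fits the stated primary objective. The objective is neutral, the test is two-sided and 63 is the two-sided number. A reader might infer from the sizing sentence and from Appendix 3 that the trial is tested only for a fall. The documents do not support that: Appendix 3 obtains 63 at alpha 0.025 in one direction, which is the usual way to size a two-sided 5% test. Nor is it true that no result could support the strategy, since a significantly higher group 2 titer would support a better response.

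Two other tempting readings also go too far. One is that the strategy must show a better response at 18 weeks and so would succeed only 2.5% of the time if nothing interferes. The summary sentence names no time point, Outcome measures also names birth as a comparison of interest, and Data analysis compares cord and 6-week titers. The other is that the Protocol plans to read a non-significant test as no interference. That rule appears nowhere, so the 20%, 46% and 70% rates describe a reading the plan leaves open, not one it prescribes.

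It is also fair to say that Table 2 discloses the limited sensitivity to smaller falls (235 per group for a 30% fall), and that the correlation and regression of 18-week on cord titers add evidence. These analyses still come with no margin or rule for concluding non-interference. The gap stands.

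**Conclusion.** The concern holds as a mismatch between sizing, analysis and intended conclusion. The 18-week comparison is justified only by a 50% fall in group 2, the recommendation depends on a better response at an unstated time, and nothing says what result would show that the infant response is preserved. The test can establish a large change in either direction (about 80% power for twofold with the 19F SD, 59% with the 6B SD). It cannot establish absence of interference: a true 30% fall is non-significant about 70% of the time.

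These figures assume 63 evaluable per group, log-normal titers with equal SDs, and US infant SDs from a different conjugate vaccine and schedule, as the Protocol itself does. The point does not depend on an arithmetic error, because the plan's 63, 50 and 90 all reproduce.

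**What to change.** 1. In Sample size estimate and Data analysis, make the 18-week result the group 2 / group 1 GMT ratio with a two-sided 95% confidence interval for each serotype.
2. Fix the reading in advance:
   - no important interference is claimed only if the lower limit exceeds a margin that the sponsor sets and justifies;
   - an interval wholly below 1 is reported as a reduction, even if it lies above the margin;
   - an interval containing both the margin and 1 is inconclusive.

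   The second rule is needed because, at 63 per group, an SD below about 0.43 would allow one interval to lie wholly between 0.5 and 1.
3. State the power for the chosen margin by serotype. The 50% difference used for sizing is a detectable difference and does not become an acceptable loss without justification. If it is adopted, say that 63 per group gives about 80% power for 19F and about 59% with the 6B SD.
4. In the opening summary, say at which time point the better response applies (for example cord and 6 weeks) and use the non-interference criterion at 18 weeks.
5. Reconcile the one-directional alternative in Appendix 3 with the two-sided test in the text.

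**Cost.** Wording only, with no extra subjects or samples if the margin is 0.5 and the lower 6B power is accepted. A tighter margin would need the larger numbers shown above. Some results will be declared inconclusive: with a 0.5 margin and a true ratio of 1, about 100 − 80 − 2.5 = 18% of the time for 19F and about 100 − 59 − 2.5 = 39% with the 6B SD.

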One hundred and eighty healthy pregnant women in their third trimester will be enrolled after informed consent. Each will be given a unique identification number, which will indicate the study group she is assigned to. The numbers assigned will be from a pre-prepared list of numbers. Randomization will be a one step block design of 4 to ensure that in each block the groups are equally represented. This will entail in the study groups will be randomised to the receiving the pneumococcal polysaccharide vaccine (study) and those in the control study groups meningococcal vaccine (25). All infants will receive the conjugate pneumococcal vaccine at 6, 10 and 14 weeks of age (Appendix 1). Both these polysaccharide vaccines have been shown to be safe in our hands in published studies in Dhaka (13,25)

The design ensures that timing of blood specimens is parallel in the 4 groups, so direct comparison of each intervention can be made. For purposes of masking, every mother receives an injection of either pneumococcal or meningococcal vaccine. As such there will be total masking from the point of safety and side effect reporting in infant immunization. The major outcome variable (antibody levels) will also be determined by a completely blinded procedure.

The single dose vaccine vials will have a study label group code 1, 2, 3,4. The study coordinator will release vaccine vials to the study field staff who will take them to the obstetric practices. After determining the study group to which the mother is allocated, the field staff will note the study group allocation on the mothers' enrollment form, and write the mother's name and subject number on the vaccine vial label, and the vial number and study group in the mother's data form. After administration of vaccine, the empty study vaccine and tetanus vaccine vials will be returned to the coordinator, who will separately record the subject numbers and study group assignment against the vial numbers. Similar procedures will be followed for the study vaccines administered to the infants. The person who generates the allocation codes will not participate in subject assignment to study groups, vaccine administration, outcome assessment or data analyses, so that these processes remain blinded.

Baseline data collection

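### The statement that 63 per group detects a 50% difference in final GMTs is supported for 19F but not for 6B, where the protocol's own SD gives about 59% power

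*Protocol*

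**What the plan says.** The protocol's section on outcome measures defines the primary endpoint by serotype-specific antibody: "The primary outcome measures are the infant serum IgG antibody titers to specific capsular pneumococcal polysaccharide", together with antibody to the carrier protein. The laboratory section lists type 6 and type 19 among the vaccine types to be assayed. The data analysis section compares the final pneumococcal GMT of groups 1 and 2 without naming a lead serotype.

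Under the sample size heading, Table 1 gives the planning data for two serotypes:

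| Serotype | N | GMT (µg/ml) | Mean log | SD of logs |
|---|---|---|---|---|
| 19F | 43 | 3.6 | 0.55882 | 0.605756 |
| 6B | 45 | 2.3 | 0.36080 | 0.767809 |

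The text presents Table 2 as built from Table 1 and concludes: "A sample size of 63 in each group will allow us to detect a difference of 50% in the final geometric mean titers". The footnote gives the conditions: "assuming alpha = 0.05, beta = 0.20, power = 80" percent. The figure of 63 stands in the two-sided column. The protocol discusses sidedness ("a one-sided test of significance is appropriate, however, a 2-sided test allows full examination of the relationships"), and the data analysis section then settles on two-sided testing: "Continuous variables will be compared between groups by two-sided T-test or Mann-Whitney U test".

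**The concern.** Table 1 offers two serotypes, yet only one reaches the calculation. Every row of Table 2 has 3.6 µg/ml, the 19F value, as its reference GMT. Appendix 3 uses a mean of 0.559, again 19F, with an SD of 0.601. The 6B mean and SD enter nothing. The conclusion is nevertheless worded for the final titers in general.

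Required sample size rises with the square of the SD, and the 6B SD is 0.767809 / 0.605756 = 1.27 times the 19F SD. A claim that just reaches 80% for 19F therefore cannot hold for 6B.

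What is at stake is whether the protocol states correctly how well it can see a lower response in infants of vaccinated mothers, which it names as one goal of the comparison. A reader who relies on the sentence would credit the 6B comparison with power that the protocol's own table does not give it.

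**Working it through.** **Inputs**
- Evaluable infants per group: n = 63 (sample size section), from "If 30% of enrolled subjects do not complete the study" and 63 / 0.7 = 90 enrolled per group.
- Allocation 1:1: "Randomization will be a one step block design of 4 to ensure that in each block the groups are equally represented".
- Effect: ratio of GMTs 0.5, so the difference in log10 titer is d = log10(2) = 0.30103.
- Two-sided alpha 0.05 (z = 1.960) and power 80% (z = 0.842).
- SDs: 0.601 (Appendix 3), 0.605756 (19F, Table 1), 0.767809 (6B, Table 1).
- Appendix 3 treats the variance as known ("The standard deviations were assumed to be known and equal"), so the normal formula is the matching one. The t-test result is given as a check.

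**Formulas**
- n per group = 2 (1.960 + 0.842)² SD² / d²
- Power = Φ( d / (SD √(2/n)) − 1.960 )
- Smallest log difference detectable with 80% power = 2.802 × SD × √(2/n)

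**Step 1: reproduce the plan's figure (19F)**
- SD 0.601: n = 62.6, rounded up to 63. Standard error = 0.601 × √(2/63) = 0.1071; power = Φ(2.811 − 1.960) = 0.803. Appendix 3 states 0.80286. Reproduced.
- SD 0.605756: n = 63.6, rounded up to 64; power at 63 = 0.797 (t-test 0.790).

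The small gap between 0.601 and 0.605756 moves n by one and is immaterial.

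**Step 2: the same calculation for 6B**
- Standard error = 0.767809 × √(2/63) = 0.1368.
- Power = Φ(0.30103 / 0.1368 − 1.960) = Φ(0.2405) = 0.595 (t-test 0.588).
- n for 80% power = 102.1, rounded up to 103 per group (t-test 104).
- Detectable log difference at 63 per group = 2.802 × 0.1368 = 0.383, a GMT ratio of 10^−0.383 = 0.41, that is, a reduction of about 59%.

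**Step 3: more favourable readings for 6B, 50% reduction**

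| Reading | Power |
|---|---|
| 63 per group, two-sided 0.05 (as planned) | 59.5% |
| 63 per group, one-sided 0.05 | 71% |
| 71 per group (79% completion, 90 × 0.79), two-sided | 65% |
| All 90 per group evaluable, two-sided | 75% |

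None of these reaches 80%. One-sided testing and no dropout together would give 84%, but that is neither 63 per group nor the planned two-sided test.

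**Step 4: uncertainty of the planning SD**

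The 6B SD comes from 45 infants. Assuming normal logs, its 95% interval is 0.767809 × √(44/χ²) at the two χ² limits on 44 degrees of freedom, or 0.64 to 0.97. Power at 63 per group then runs from about 76% down to 41%. It stays below 80% throughout.

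**The case against.** The strongest reply is that nothing is miscalculated. The 63 and the 0.80286 both reproduce, and an attentive reader can see from the 3.6 µg/ml in Table 2 and the 0.559 in Appendix 3 that the basis is 19F. This stands: the fault is an unqualified generalisation, not an arithmetic slip. It does not remove the fault, because no text limits the sentence to 19F or makes 19F the lead serotype, and the table that feeds the calculation contains the SD that contradicts the wider claim.

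It is also fair to say that 59% is a planning point estimate. The data come from US infants given a different, 5-valent conjugate at 2, 4 and 6 months, and the two SDs do not differ clearly (F = 0.767809² / 0.605756² = 1.61 on 44 and 42 degrees of freedom, two-sided p = 0.13). That is a reason to label the figure as a planning estimate. The claim for 19F rests on the same source.

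A reader might infer more than the documents support:
- That the claim holds for 19F alone. It is shown to fail only for 6B. Types 1 and 23 and carrier-protein antibody have no stated SD, so their power is unknown, not shown to be low.
- That a non-significant 6B result is likely under a true halving. Its probability is about 41% (1 − 0.59), so significance remains the more probable result.
- That such a result would be taken as absence of inhibition. The protocol gives no such rule, and it adds correlation and regression analyses of cord against final titers. Those do not repair the power of the GMT comparison, but the misreading would be the reader's own.
- That the chance of detecting both serotypes is 0.797 × 0.595 = 47%. This assumes independence, and the protocol does not require significance on both.
- That the 30% assay coefficient of variation for 6B is further proof. It describes a control serum run during a study of adults, whereas the SD in Table 1 is the total spread between infants and should already contain assay noise.

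**Conclusion.** The point holds in limited form. At 63 evaluable infants per group, two-sided 0.05, the power to detect a 50% reduction in final GMT is about 80% for 19F, as stated, and about 59% for 6B, the other serotype in the protocol's planning table. For 6B, 80% power applies to a reduction of about 59% (ratio 0.41). These figures rest on the SDs in Table 1, equal variances, log-normal titers and 1:1 allocation. The shortfall for 6B does not depend on one-sided or two-sided testing at 63 per group, on the normal or t calculation, or on where the SD lies within its 95% interval. Nothing can be concluded for the remaining antigens.

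**What to change.** In the sample size section, replace the general sentence with a statement by serotype: 63 evaluable infants per group give 80% power (two-sided 0.05) for a 50% reduction in 19F and about 59% power for the same reduction in 6B, for which 80% power applies to a reduction of about 59%. Label these as planning estimates from the SDs in Table 1, and say that the calculation of 63 rests on 19F. This describes what was calculated; it does not choose a primary serotype.

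Add a 6B row to Table 2: GMT 1.15 against 2.3 µg/ml, −50%, 0.5-fold, 81 per group one-sided and 103 two-sided.

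The cost is one sentence and one table row, and a less favourable stated power. Enrolment, design and analysis stay as they are. For scale only, full power for 6B would take 103 / 0.7 = 147.1, so 148 enrolled per group or 296 pairs instead of 180; the correction does not require this.
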